#### **HES Administration Prior to Admission to the Hospital (DUS Study Site)**

- HES administration at day of admission or preceding day before admission to the hospital (yes/no/no information available);  
if yes:
  - Place/institution [hospital, ambulance, other],
  - Trade name of any prescribed HES product
  - Posology (Dosage)
    - HES infusion (first to last bag/bottle)
      - Start of infusion (Day 1/Time hh:mm)
      - Total amount infused (ml)
      - End of infusion (Day X/Time hh:mm)

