The retrospective data collection will comprise patient chart data of patients who have been treated between January 1st, 2015 and May 1st, 2015. Patient chart data will be collected going backwards in a predefined timeframe, e.g. of one week (depending on the results of the site feasibility), starting May 1st, 2015 (calendar week 18). All patients treated with HES-containing products of Fresenius Kabi during this week should be documented. In the event that the predefined number of patients per site is not achieved within e.g. this week, data collection can be extended e.g. week by week (again going backwards) until the number of predefined patients has been reached, but not beyond January 1st, 2015. All patients treated with HES-containing products of Fresenius Kabi within the predefined timeframe are documented in the DUS and followed-up until the start and end of HES therapy, even if the start or end of HES therapy are outside the predefined timeframe.

Data collection will include relevant demographic data, main diagnosis at hospital admission, indication for HES use, posology (dosage), and co-morbidities.

The parameters as listed in [Section 9.3](#) will be documented.

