#### **HES Administration in the Hospital (DUS Study Site)**

- Trade name of prescribed HES product
- Posology (Dosage)
  - HES infusion (first to last bag/bottle)
    - Start of infusion (Day Y/Time hh:mm) of each bag/bottle
    - Amount infused (ml) of each bag/bottle
    - End of infusion (Day Z/Time hh:mm) of each bag/bottle

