## **9.7 Data Analysis**

### **9.7.1 Descriptive Data**

Because of the exploratory character of this study only descriptive statistics will be performed. All parameters ([see Section 9.3](#)) will be presented as mean ± standard deviation for continuous normally distributed variables and median (25th; 75th percentile) for ordinal and continuous non-normal (skewed) variables. Categorical variables will be presented as percentage (and 95 % confidence interval). All analyses will be performed for the overall population as well as for each country separately. All data will be examined for the overall population and subgroups (each site/country separately) specified by indication and contraindications according to the revised PI (as listed in Annex III of the EC decision).

The number of patients (including percentage, 95 % confidence intervals) receiving HES-containing medicinal products that do not adhere to the specifications made in the revised PI will be examined.

Cumulative and maximum daily dose will be calculated for analysis of exposure to HES products.

Coverage of HES treated patients (i.e. the estimated proportion of all HES administrations that are included in the DUS population in each site) will be estimated for each site. The variable 'average HES amount used per week' will be used to estimate the total HES population treated with products of Fresenius Kabi of each site, which is the denominator of the coverage rate.

Missing data in the eCRF will be detected via automatic edit checks by the electronic data capture system, during data entry, to assess whether the information is available in the PDMS or patient chart. Data that remain missing will not be imputed in the statistical analyses.

Prior to database closure a detailed statistical analysis plan (SAP) will be written to describe how the data will finally be analysed.

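### One lump total for pre-admission HES only bounds the maximum daily dose when the record spans more than one calendar day, and HES given only before the two-day look-back is not counted

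*Protocol*

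**What the plan says.** Four places in the protocol bear on this.

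- Section 9.3.2, under the sub-heading on HES before admission to the study site, asks about "HES administration at day of admission or preceding day before admission to the hospital". The answers are yes, no, or no information available. A yes opens a dosage block that runs from the first to the last bag, with one start (day and clock time), one total volume in ml and one end (day and clock time).
- Section 9.3.2, under the sub-heading on HES in the study hospital, asks for start and end times and "Amount infused (ml) of each bag/bottle".
- Section 9.1 says that every included patient is "followed-up until the start and end of HES therapy, even if the start or end of HES therapy are outside the predefined timeframe".
- Section 9.7.1 says: "Cumulative and maximum daily dose will be calculated for analysis of exposure to HES products". It adds that data still missing after the edit checks are not imputed.

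Posology is one of the three adherence outcomes (Sections 8 and 9.1). No section says how a pre-admission total is to be split over days.

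**The concern.** The dose variables have to be built from two records of different resolution. The hospital record can be cut at midnight; the pre-admission record cannot, although the question that opens it covers two calendar days. For a patient already on HES on arrival, the admission day is where the two records must be added, so the split matters most there.

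The look-back raises a second problem. If all earlier HES was given two or more days before admission, the correct answer is no, and therapy appears to begin at the study site. The field is validly completed, so the checks for missing values in Sections 9.7.1 and 9.8.2 have nothing to detect.

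Section 9.3.2 fixes which data are collected. An analysis plan can choose a rule for handling the total, but it cannot recover a daily volume that was never recorded.

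**Working it through.** **The plan's own figure.** The protocol gives no figure on dose capture. Its precision example in Section 9.5 reproduces with the exact binomial interval: 10/334 gives 1.4 % to 5.4 %, and 90/3000 gives 2.4 % to 3.7 %. It serves below only as a yardstick.

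**Assumptions.** Daily means calendar day, and the day labels of the two records run on a common count. The volumes are illustrative. The dose limits of the product information are not reproduced in the protocol text, so none is applied.

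**1. Pre-admission record alone.** Let T be the total and k the number of calendar days it spans. The largest of k non-negative daily volumes summing to T is at least their mean and at most the whole:

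T/k ≤ maximum daily dose ≤ T

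- T = 1000 ml, k = 1: exactly 1000 ml
- T = 1000 ml, k = 2: 500 to 1000 ml
- T = 2000 ml, k = 2: 1000 to 2000 ml
- T = 2000 ml, k = 3: 667 to 2000 ml

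The cumulative dose within the record is T, exactly, in every case.

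**2. Adding the study site's bags.** Take T = 2000 ml running from the evening before admission to the next morning, and 1000 ml in site bags later on the admission day. Let x be the part of T given on the preceding day, from 0 to 2000 ml.

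- Admission-day dose = (2000 − x) + 1000 = 3000 − x, so 1000 to 3000 ml.
- Maximum daily dose over the two days = the larger of x and 3000 − x. It is smallest at x = 1500 (1500 ml) and largest at x = 0 (3000 ml).
- Cumulative dose = 2000 + 1000 = 3000 ml, exactly.

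Any daily limit inside the range for the maximum leaves the patient unclassified. If T had all been given on the admission day, the dose would be exactly 3000 ml.

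**3. HES before the look-back.** Let E be the volume given only before the two-day window. Then recorded cumulative dose = true cumulative dose − E, which is too low whenever E > 0. E cannot add to the admission-day dose, because it was given at least two days earlier. The recorded maximum daily dose is affected only if one of those earlier days carried the largest dose.

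**4. Effect on an adherence rate.** The share of patients with pre-admission HES is not in the protocol. Purely as an assumption, let f = 1 % to 10 % of patients have it, and let m = 5 % to 20 % of those be misclassified on posology. Starting from the 3 % planning rate:

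- If breaches are missed, observed rate = 3 % − f × m. This gives 3 − 0.05 = 2.95 % (1 % × 5 %) down to 3 − 2 = 1.0 % (10 % × 20 %).
- If a multi-day total is booked to one day and creates false breaches, observed rate = 3 % + f × m, from 3.05 % up to 5.0 %.

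Against a country interval of 1.4 % to 5.4 %, the effect runs from negligible to about the distance from 3 % to either limit. Its sign depends on a rule the protocol does not state.

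**The case against.** The strongest case for the protocol is that the two-day window is only a trigger question. A patient treated for three days up to transfer had HES on the preceding day, so the answer is yes. The dosage block can then be read as reaching back to the first bag, with its start day and time. Ambulance HES on the day of arrival falls on one calendar day and gives an exact daily dose. A single total is also reasonable for treatment given elsewhere, since bag-level detail may not be in the site's chart. The timeframe in Section 9.1 is the calendar collection window, not a promise to reconstruct care at other institutions. Section 9.9 already concedes that amounts may be underestimated.

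Much of this stands. A reader might infer that the start of HES therapy cannot be derived for transferred patients. The protocol does not support that: with a yes, the start is a field. It is lost only if all earlier HES precedes the window, if no information is available, or if sites cut the record at the window, which the wording leaves open. Section 9.1 is in tension with the look-back rather than in plain contradiction, partly because HES therapy is not defined across a gap or a transfer.

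Two things survive. A record spanning several calendar days loses its daily split even when the transfer papers are complete. HES given only before the window is dropped without a flag. Section 9.9 attributes underestimation to incomplete documentation, which is a different cause.

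**Conclusion.** The point holds in a limited form. For patients whose pre-admission record spans more than one calendar day, the promised maximum daily dose is bounded (T/k to T before site bags are added) but not identifiable. For patients whose HES before admission lay wholly outside the look-back, cumulative dose is understated if that HES belongs to the same episode. Patients whose pre-admission HES fell on a single calendar day within the look-back are unaffected for daily dose.

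A reader might go on to infer that posology adherence is overstated. That is not established: unseen earlier HES pushes that way, but booking a multi-day total to one day pushes the other way. Nor does the protocol give the share of patients affected, or show that they are more severely ill than the rest.

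The conclusion rests on reading daily as calendar day. If any 24-hour period were meant, a pre-admission record and site bags lying wholly within 24 hours would give an exact dose, and the problem would be confined to longer spans.

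**What to change.** Reconcile Section 9.1, the pre-admission item in Section 9.3.2, and the dose variables in Section 9.7.1:

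- Record pre-admission HES per bag, as for the study site, or per calendar day where the transfer record gives only totals.
- Ask for it back to the first documented HES administration of the current episode, where the chart shows it. Define that episode for data-collection purposes, and say whether the two-day question is a trigger or a limit.
- State whether daily means a calendar day or any 24-hour period.
- Where the split remains unknown, report maximum daily dose as not assessable, give the number of such patients, and show the lower and upper bounds.

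The cost is a few eCRF fields that open only for patients with pre-admission HES. The downside is that some transfer records will lack the detail, so some patients will be classed as not assessable. Sample size and clinical management are untouched.

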#### **HES Administration in the Hospital (DUS Study Site)**

- Trade name of prescribed HES product
- Posology (Dosage)
  - HES infusion (first to last bag/bottle)
    - Start of infusion (Day Y/Time hh:mm) of each bag/bottle
    - Amount infused (ml) of each bag/bottle
    - End of infusion (Day Z/Time hh:mm) of each bag/bottle

#### **At Completion of HES Administration**

- Date of discharge from treating ward (calendar week, year)

## 9.4 Data Sources

Data entry based on patient charts, preferably from electronic PDMS, will be performed by the investigators or delegated responsible persons at the participating site using the online eCRFs.

The eCRFs will be structured according to the parameters described in [Section 9.3](#).

## 9.5 Study Size

For determining the number of patients that should be documented in this DUS it is aimed to achieve sufficient precision of estimates for the percentage of non-compliance to the PI. It is intended that all analyses will be performed for the overall population as well as for each country separately. Therefore, the chosen sample size needs to have sufficient precision also for the country-specific estimates.

For potential non-compliance rates in the interval of 1 % to 4 % the expected precision (95 % confidence intervals) for various sample sizes ranging from 100 to 3000 patients were calculated. The results are shown in Table 1.

Table 1: Expected 95 % confidence intervals for potential non-compliance rates in the intervals of 1 % to 4 % estimated in sample sizes of 100 to 3000 patients. Exact method (R function `binom.test{stats}`) used.

	Estimated rate 1 %	Estimated rate 2 %	Estimated rate 3 %	Estimated rate 4 %
N = 100	0.0 - 5.4 %	0.2 - 7.0 %	0.6 - 8.5 %	1.1 - 9.9 %
N = 334	0.2 - 2.6 %	0.8 - 4.3 %	1.4 - 5.4 %	2.1 - 6.6 %
N = 500	0.3 - 2.3 %	1.0 - 3.6 %	1.7 - 4.9 %	2.5 - 6.1 %
N = 1000	0.5 - 1.8 %	1.2 - 3.1 %	2.0 - 4.3 %	2.9 - 5.4 %
N = 1500	0.6 - 1.6 %	1.4 - 2.8 %	2.2 - 4.0 %	3.1 - 5.1 %
N = 2000	0.6 - 1.5 %	1.4 - 2.7 %	2.3 - 3.8 %	3.2 - 5.0 %
N = 2500	0.6 - 1.5 %	1.5 - 2.6 %	2.4 - 3.7 %	3.3 - 4.8 %
N = 3000	0.7 - 1.4 %	1.5 - 2.6 %	2.4 - 3.7 %	3.3 - 4.8 %

Considering the number of patients that is expected per country, it is intended to include at least 3000 patients in total (meaning 334 patients per country) in order to achieve sufficient precision of also country-specific estimates.

As an example, for an assumed non-compliance rate of 3 % and a sample size of 334 patients the expected 95 % confidence interval is 1.4 % to 5.4 %. For the intended sample size of overall 3000 patients the expected 95 % confidence interval is 2.4 % to 3.7 %.

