### 9.2.1 Countries, Feasibility and Site Selection

The DUS is intended to be conducted in the following European Member States: Belgium, Czech Republic, France, Germany, Netherlands, Poland, Spain, Sweden, United Kingdom. In order to reduce potential bias from site specific clinical practice it is aimed that per country, at least 5 sites will be included expecting a minimum of about 67 eligible patients per site (depending on the outcome of the feasibility). The sites can only participate upon agreeing to the requested procedures in the participating sites as specified in [Section 9.8.1](#).

Prior to the start of the DUS, a feasibility check/survey will be performed by the CRO to evaluate e.g.

- whether the sites use HES-containing medicinal products from Fresenius Kabi,
- how frequently HES-containing medicinal products from Fresenius Kabi have been used,
- whether the sites use electronic PDMS,
- whether all wards or, if this is not the case, which wards in the hospitals use electronic PDMS,
- which wards have been supplied with HES from Fresenius Kabi within the sites,
- whether the sites collect general consent for using patients' data for research projects,
- whether the sites are willing to participate.

For the retrospective data collection in this DUS, sites using electronic PDMS will be preferred since PDMS allow the comprehensive review of all patient charts at the site regarding administration of HES products in the given retrospective data collection period. Thus, the selection process for sites using HES-containing medicinal products from Fresenius Kabi will be performed following a hierarchic stepwise process as described below:

- (1) HES use and full PDMS coverage within data collection period
- (2) HES use and PDMS use in all wards which have been identified in the survey to be supplied with HES within data collection period
- (3) HES use and PDMS use or paper documentation in all wards which have been identified in the survey to be supplied with HES within data collection period (applies to sites with partial PDMS coverage in HES using wards)
- (4) Sites or wards with HES use within data collection period but paper documentation only

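### The expected precision in Section 9.5 treats patients as independent although they come in site clusters of about 67, so Table 1 is too optimistic unless between-site variation is negligible

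*Protocol*

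**What the plan says.** Section 9.5 rests the study size on interval width: "the expected precision (95 % confidence intervals) for various sample sizes ranging from 100 to 3000 patients were calculated". The note to Table 1 gives the method: "Exact method (R function `binom.test{stats}`) used". Country results drive the choice, since "the chosen sample size needs to have sufficient precision also for the country-specific estimates". The worked example takes a 3 % rate. For one country it reads "a sample size of 334 patients the expected 95 % confidence interval is 1.4 % to 5.4" %, and for the whole study "overall 3000 patients the expected 95 % confidence interval is 2.4 % to 3.7" %. No ICC, design effect or other allowance for sites appears in the section.

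Section 9.2.1 describes how patients are obtained: "at least 5 sites will be included expecting a minimum of about 67 eligible patients per site", subject to feasibility. It also gives the reason for using several sites: "In order to reduce potential bias from site specific clinical practice it is aimed that per country, at least 5 sites will be included".

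For the analysis, Section 9.7.1 promises percentages with 95 % confidence intervals, overall and by country and site. It names no interval method and leaves the detail to a SAP written before database closure. Section 9.9 lists bias from hospital selection as a limitation but does not mention correlation within sites.

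**The concern.** The outcome is whether hospital physicians follow the product information. Patients in one hospital share prescribers, local protocols and case mix, so their outcomes tend to resemble each other. Section 9.2.1 accepts this when it asks for several sites because of site-specific practice. Section 9.5 then calculates as if each of the 334 patients were a separate draw from the country.

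With any positive correlation within sites, 334 patients from five hospitals tell less about a country than 334 independent patients would. At stake is the precision presented to the regulator for a study meant to evaluate risk minimisation. A country rate could look well determined when it mainly reflects the habits of one or two hospitals.

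**Working it through.** **1. Reproduce the protocol's figures.** The interval is Clopper-Pearson: lower limit = Beta(0.025; x, n−x+1), upper limit = Beta(0.975; x+1, n−x), with x = n × rate rounded to a whole patient.

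- n = 334, 3 %: x = 10, interval 1.44–5.44 % (stated 1.4–5.4 %).
- n = 3000, 3 %: x = 90, interval 2.42–3.67 % (stated 2.4–3.7 %).

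All 64 limits in Table 1 reproduce to one decimal. The arithmetic is correct, and no hidden allowance for clustering sits in the numbers.

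**2. Inputs for the clustered calculation.**

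- Patients per site m: about 67 (Section 9.2.1; 334/5 = 66.8).
- Sites: 5 per country at the minimum, so 9 × 5 = 45 overall.
- ICC: not in the protocol. Assumed range 0.01 to 0.05, with 0.005 as a low case.

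Design effect DE = 1 + (m − 1) × ICC = 1 + 66 × ICC. Effective n = n / DE. The exact interval is then taken at effective n and 3 %.

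| ICC (assumed) | DE | Effective n, country | Interval, country | Effective n, overall | Interval, overall |
|---|---|---|---|---|---|
| 0 (protocol) | 1.00 | 334 | 1.4–5.4 % | 3000 | 2.4–3.7 % |
| 0.005 | 1.33 | 251 | 1.3–5.9 % | 2256 | 2.3–3.8 % |
| 0.01 | 1.66 | 201 | 1.1–6.4 % | 1807 | 2.3–3.9 % |
| 0.02 | 2.32 | 144 | 0.9–7.3 % | 1293 | 2.1–4.1 % |
| 0.05 | 4.30 | 78 | 0.5–9.6 % | 698 | 1.9–4.6 % |

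To judge these ICCs: the between-site SD of the true rate is √(ICC × 0.03 × 0.97). That is 1.7 percentage points at ICC 0.01 and 3.8 at ICC 0.05, around a mean of 3 %.

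**3. Small-sample correction.** Five sites give 5 − 1 = 4 degrees of freedom for one country. The Korn-Graubard interval multiplies effective n by (t with n − 1 df / t with cluster df)². For a country this is (1.967/2.776)² = 0.50.

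- ICC 0.01: 201 × 0.50 ≈ 101, interval about 0.6–8.5 %.
- ICC 0.05: 78 × 0.50 ≈ 39, interval about 0.1–14.2 %.
- Even at ICC 0: 334 × 0.50 ≈ 168, interval about 1.0–6.8 %.

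The table in step 2 is therefore the favourable version for countries.

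**4. Coverage if an unadjusted exact interval were also used in the analysis.** Site rates were drawn from a beta distribution with mean 3 % and the assumed ICC, with binomial counts within sites and 100,000 runs.

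| ICC (assumed) | Country, 5 sites | Overall, 45 sites |
|---|---|---|
| 0 | 98 % | 95–96 % |
| 0.005 | 95 % | 91–92 % |
| 0.01 | 92–93 % | 88–89 % |
| 0.02 | 87 % | 81–82 % |
| 0.05 | 73–74 % | 66–68 % |

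The ranges reflect simulation error and, overall, whether 3000 or 45 × 67 = 3015 patients are simulated.

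**The case against.** Several points on the other side have force.

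- **The analysis method is open.** The binomial routine is named only for the planning table. Section 9.7.1 names no interval method and defers to a SAP that is not at hand. A reader might infer that the reported intervals will be too narrow. The protocol does not support that: it follows only if unadjusted binomial intervals are used. This stands, and the coverage figures are conditional for that reason.
- **The ICC is assumed.** At 0.005 the unadjusted country interval still covers about 95 %, because the exact method is conservative, although the overall interval falls to about 91–92 %. At 0.05 the between-site SD exceeds the mean rate, and nothing in the protocol supports or excludes this. This stands as a limit on the size, not on the direction.
- **Precision is not the sole ground for the size.** A reader might take it so, but Section 9.5 also refers to the number of patients expected per country. Five sites is a minimum, and Section 9.2.1 allows new sites if recruitment falls short. More and smaller sites would reduce the design effect.
- **The study is descriptive.** Section 8 excludes testing of prespecified hypotheses, and Section 9.7.1 examines sites separately, so a deviant hospital could be seen. This lessens the harm but does not correct the precision figures.
- **Table 1 ends at 4 %.** A reader might infer that this is too low for non-compliance of any kind. The protocol calls these potential rates and does not say that a combined rate lies among them. A higher figure would need invented component rates, so no complaint is made here.

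None of this restores Section 9.5. Its figures are already stated, by a named method that assumes independence, for a design that the protocol itself describes as affected by site practice.

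**Conclusion.** The point holds for the planning figures. Table 1 and the worked example describe independent patients, and the design does not supply them. The direction is certain for any positive ICC. The size depends on an ICC that the protocol does not give.

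Over the assumed 0.01 to 0.05, with 5 sites of about 67 per country, a country's upper limit at 3 % moves from 5.4 % to between 6.4 % and 9.6 %. The overall upper limit moves from 3.7 % to between 3.9 % and 4.6 %. Both are before small-sample correction, which widens the country intervals much further. Whether the final report will understate uncertainty cannot be decided from the protocol.

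**What to change.** Keep 334 per country and 3000 overall.

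1. In Section 9.5, state that the present Table 1 and example assume no correlation within sites. Add intervals with a design effect over a stated ICC range, for example 0.01 to 0.05 at about 67 patients per site.
2. In Section 9.7.1 or the SAP, specify that country and overall intervals use site as cluster and country as stratum, with a method suited to few clusters. Report the observed ICC.
3. Make the restated table match the chosen method. If that is Korn-Graubard with 4 degrees of freedom for a five-site country, the 3 % row should show about 0.6–8.5 % at ICC 0.01 and 0.1–14.2 % at ICC 0.05, not the design-effect-only intervals.

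The cost is a replaced table, some wording and a few lines of analysis code, with no extra patients. The drawbacks are that the stated precision becomes less favourable, and that a design effect estimated from about five sites is itself unstable, which the report should say.
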